All patients in the Full Analysis Set (FAS) will be included in the primary analysis, i.e., the number of confirmed relapses observed up to the end of patient's participation in the study. Relapses will be counted regardless of whether a patient is on or off study drug. Therefore it is expected that all randomized patients can contribute to the primary analysis. The primary analysis model adjusts for missing information (early study discontinuations) under some statistical assumptions (non-informative dropouts and constant ARR).

The response variable for this analysis is the number of confirmed relapses for each patient, and the quadratic variance estimate will be used. The natural log of (time in study for each patient) will be used as the offset to account for the varying lengths of patients' time in the study. The null hypothesis will be rejected if the observed p-value is less than the significance level of 0.05.

The Extension Phase is designed to obtain long-term safety, tolerability and efficacy data in patients treated with fingolimod. The study will also examine the safety, tolerability and effectiveness of converting patients from interferon- β -1a treatment in the Core Phase to fingolimod treatment in the Extension Phase.

1 Introduction

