9.1 Analysis sets

Core Phase:

All screened subjects (SCR): The SCR set comprises all subjects who were screened. The SCR will be used only for the summary of screening failures.

Randomized set (RAN): The RAN set comprises all subjects who were assigned a randomization number. The RAN will be used for the summaries of subject disposition, protocol deviation, demographic, baseline characteristics, and medical history data.

Full Analysis Set (FAS): The FAS comprises all randomized subjects with assigned treatments who took at least one dose of study medication. Subjects will be analyzed according to the randomized treatment assignment following the intention-to-treat principle, even if they actually received a different treatment. The FAS will be used for all efficacy analyses.

Per-protocol set: Consists of all patients in the full-analysis set who do not have any major protocol deviations that could confound the interpretation of analyses conducted on the FAS. Major protocol deviations will be determined according to the predefined protocol deviation criteria before treatment unblinding. Any efficacy data after study drug discontinuation will

be excluded. The per-protocol set will only be used for the supportive analyses of the primary efficacy variable.

Safety Set: The safety set includes all patients who received at least one dose of study medication. Subjects will be analyzed according to the actual treatment received. The Safety Set will be used for all safety analyses.

Fingolimod Extension Phase:

Extension Phase enrolled set: Includes all patients who were enrolled in the Extension Phase, whether or not they actually took any extension study medication. The Extension Phase enrolled set will be used for the summaries of subject disposition, protocol deviations, demographic, baseline characteristics, and medical history data.

Extension Phase FAS: All patients who *entered the Extension Phase* and received at least one dose of extension study medication. Patients will be analyzed according to the randomized treatment in the Core Phase. This analysis set will be used for all within-group efficacy analyses.

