3.1 Analysis sets

All screened subjects (SCR): The SCR set comprises all subjects who were screened. The SCR will be used only for the summary of screening failures.

Randomized set (RAN): The RAN set comprises all subjects who were assigned a randomization number. The RAN will be used for the summaries of subject disposition, protocol deviation, demographic, baseline characteristics, and medical history data.

Full Analysis Set (FAS): The FAS comprises all randomized subjects with assigned treatments who took at least one dose of study medication. Subjects will be analyzed according to the randomized treatment assignment following the intention-to-treat principle,

even if they actually received a different treatment. The FAS will be used for all efficacy analyses.

Safety Set (SAF): The safety set includes all subjects who received at least one dose of study medication. Subjects will be analyzed according to the actual treatment received. The Safety Set will be used for all safety analyses. Subjects will be analyzed according to the treatment they are assigned to at randomization unless a subject takes non-randomized study medications and does not take any study medication as randomized, in that case the subject will be analyzed according to the treatment actually taken.

Per-protocol set (PPS): The PPS is a subset of FAS, consists of all randomized subjects who take at least one dose of study medication and have no major protocol deviations that could confound the interpretation of analyses conducted on the FAS. Major protocol deviations will be determined according to the pre-defined protocol deviation criteria before treatment unblinding. For analyses performed on the PPS, any efficacy data assessed after permanent discontinuation of study medication will be excluded. The PPS will primarily be used for the supportive analyses of the primary efficacy variable and the key secondary variable.

Follow-up set (FUS): The FUS consists of all subjects in the safety set who have at least one visit or who have AE, MS relapse, or concomitant medication starting after study drug discontinuation, but before first dose of the extension study medication (if applicable). Subjects will be grouped in the same way as described above for the analysis on the safety set. Only the safety follow up data analysis will be performed on the follow-up set.

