Subject classification in the analysis sets is entirely based on protocol deviation and non-protocol deviation criteria. A list of protocol deviations are specified prospectively in the Edit Check Specification. A subset of these protocol deviation criteria results in the exclusion of the subjects from analysis.

Table 3-1 provides a list of pre-defined protocol deviations considered important enough to lead to exclusion of a subject from an analysis set. These are taken from the Edit Check Specifications.

Table 3-1 Specifications of important protocol deviations

Deviation ID	Description of deviation	Excl. from analysis dataset				
		SCR	RAN	FAS	SAF	PPS
I01	Informed consent was not obtained. However, study assessments were performed.	X	X	X	X	X
E01	Patient has progressive multiple sclerosis. However, patient was randomized.			X		X
E04	Patient fulfills either the definition of ADEM or the criteria for neuromyelitis optica. However, patient was randomized.					X
E04A	Any patient is positive for aquaporin 4 at Screening. However, patient was randomized					X
E05B	Patient was treated with high dose intravenous immunoglobulin within 2 months prior to randomization. However, patient was randomized.					X

Deviation ID	Description of deviation	Excl. from analysis dataset				
		SCR	RAN	FAS	SAF	PPS
E05E	Any patient previously treated with excluded immunosuppressive or DMT medications within per protocol (Amend 4 or higher criteria) specified time windows at any time. However patient was randomized.					X
E05F	Patient has been previously treated with fingolimod at any time. However patient was randomized.					X
E26	Patient took study drug or therapy within 180 days or 5 half-lives of Randomization, whichever is longer. However, patient was randomized.					X
I03	Central MRI review completed and diagnosis of MS not confirmed. However, patient was randomized.			X		X
I04B	Number of relapses within: 1 yr prior to randomization is < 1, or 2 yrs prior to randomization is < 2; or 6 mths no Gd lesions. However patient was randomized.					X
I05	EDSS score at screening/baseline was greater than 5.5. However, patient was randomized.					X
M01	Patient used immunosuppressive medication during double blind treatment					X
O02 ¹	Site did not follow per protocol blinding procedures such that the integrity of the study may have been compromised.					X
O02A ¹	Sponsor provided potentially unblinding information to the site that could have compromised the integrity of the study.					X

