4.2.1.2 Handling dropouts/censorings in ARR calculations

The primary NB model with an offset for the time in study adjusts for various treatment duration and missing information (drop-out or censoring at the time of study completion) under the assumption of non-informative drop-out, information missing at random, and constant relapse rate over time. According to the protocol, subjects who discontinue study treatment should remain in the study and follow the assessment schedule. All subjects in the FAS will be included in the primary analysis, i.e., the number of confirmed relapses observed up to the end of subject’s participation in the study. Relapses will be counted regardless of whether a subject is on or off study drug.

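### SAP Table 3-1 removes progressive-MS and unconfirmed-MS patients from the FAS, which protocol 9.1 does not do; per-protocol rule I04B also joins its failures with *or* where *and* is needed (minor)

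*SAP*

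**What the plan says.** Protocol 9.1 defines the FAS without any deviation exclusion: "The FAS comprises all randomized subjects with assigned treatments who took at least one dose of study medication". Patients are analysed as randomised, under intention to treat. In the same section, deviations enter only through the per-protocol set (PPS), which keeps FAS patients who "do not have any major protocol deviations that could confound the interpretation of analyses conducted on the FAS".

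SAP 3.1 repeats the FAS definition and adds "The FAS will be used for all efficacy analyses". SAP 4.2.1.2 says "All subjects in the FAS will be included in the primary analysis".

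Still within SAP 3.1, the text leading into Table 3-1 says that set membership is decided from deviation and non-deviation criteria, and that the table lists the deviations that remove a subject from a set. Three rows carry a mark under FAS:

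- Row I03 is marked under FAS and PPS but not under the other three sets. It reads "Central MRI review completed and diagnosis of MS not confirmed. However, patient was randomized".
- Row E01 has the same two marks. It reads "Patient has progressive multiple sclerosis. However, patient was randomized".
- Row I01 is marked under all five sets. It reads "Informed consent was not obtained. However, study assessments were performed".

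Every other row removes from the PPS only. One of these is I04B. It flags fewer than one relapse in the year before randomisation, or fewer than two in the two years before randomisation, or no Gd-enhancing lesion in six months. The inclusion criterion behind it (protocol 4.1) is met by any one of three routes: one relapse in the past year, two in the past two years (relapses counted back from screening), or a Gd-enhancing lesion within six months before randomisation.

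**The concern.** A dosed patient with an E01 or I03 deviation belongs to the FAS under protocol 9.1 and is outside it under SAP Table 3-1. The FAS carries the primary test, the key secondary test and the other efficacy analyses, so the two documents give different confirmatory populations.

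Both deviations are failures of entry eligibility (protocol 4.1, central review of the diagnosis; protocol 4.2, exclusion criterion 1), and the protocol's FAS does not remove entry failures. If the sponsor intends an exception, its conditions are not written. The requirement to settle deviations before unblinding stands in the PPS definition only, and row E01 states no time point or assessor.

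I04B is a separate and smaller matter. Negating a criterion that any one of three routes can satisfy requires all three to fail. Joined with *or*, the rule would drop eligible patients from the supportive PPS analyses.

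**Working it through.** **1. Set membership.** Take a randomised, dosed patient with E01 or I03.

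- Protocol 9.1: in the FAS; out of the PPS if the deviation is judged major.
- SAP 3.1 definition: in the FAS.
- SAP Table 3-1: out of the FAS and PPS; in RAN and SAF.

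The first and third cannot both be followed. I01 differs in kind: it removes the patient from all five sets on consent grounds, although the FAS definition does not state this exception.

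**2. Reproducing the plan's information figure.** Inputs from protocol 9.6: ARR 0.18 (fingolimod) and 0.36 (IFN β-1a), T = 2 years, κ = 0.82, n = 95 per arm, two-sided alpha 0.05. Protocol Appendix 5, Equation 2:

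I = n / {1/(λ1T) + 1/(λ2T) + 2κ} = 95 / (2.7778 + 1.3889 + 1.64) = 16.3605, against 16.36 stated.

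Power = Φ(ln 2 × √I − 1.96) = Φ(2.8037 − 1.9600) = 80.06%, against 80% stated.

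**3. Removing patients.** The number with E01 or I03 is not in the documents; 1 to 4 of 190 is an assumption. With unequal arms and equal follow-up, Equation 1 gives

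I = 1 / [(1/0.36 + 0.82)/n1 + (1/0.72 + 0.82)/n2] = 1 / [3.5978/n1 + 2.2089/n2],

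where n1 is fingolimod and n2 is IFN β-1a.

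| Removed | n1 / n2 | Information | Power |
|---|---|---|---|
| 0 | 95 / 95 | 16.36 | 80.06% |
| 1 | 95 / 94 | 16.29 | 79.90% |
| 1 | 94 / 95 | 16.25 | 79.80% |
| 4 | 95 / 91 | 16.09 | 79.40% |
| 4 | 93 / 93 | 16.02 | 79.22% |
| 4 | 91 / 95 | 15.93 | 79.00% |

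The largest loss of information is 1 − 15.9267/16.3605 = 2.65%.

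**4. I04B as logic.** Three routes, each met or not, give 2³ − 1 = 7 combinations that satisfy the inclusion criterion. Read literally with *or*, I04B spares only the combination that meets all three and flags the other 6. Everyone who entered on MRI activity alone is flagged, because both relapse routes fail. With *and*, it flags none of the 7. These are logical combinations, not patients; the share of patients affected cannot be derived.

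**The case against.** **The rule is pre-specified and visible.** SAP 3.1 says that deviation criteria determine set membership, so its general definition and Table 3-1 can be read as rule and exceptions. Set sizes by arm (SAP 3.2) and PPS-excluding deviations by arm (SAP 3.3) will be reported, so any removal would show. This stands, and it weakens the conflict inside the SAP. It does not remove the conflict with protocol 9.1, which has no such exception for the FAS.

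**The group may be empty.** Progressive MS is an exclusion criterion and central review precedes randomisation, so each deviation needs a failed entry gate. This stands and is the main reason for rating the point minor.

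**Tempting stronger readings.** A reader might take the sentence in the protocol synopsis and section 9.4.3, "Therefore it is expected that all randomized patients can contribute to the primary analysis", as forbidding any exclusion. It follows from counting relapses on or off study drug and concerns treatment discontinuation. Nor can it be literal, because the protocol's own FAS leaves out randomised patients who were never dosed. The point therefore rests on section 9.1.

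A reader might also infer bias in the treatment comparison. Both deviations concern status at entry, and nothing in the documents shows removal depending on treatment or outcome.

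A reader might infer that the trial becomes underpowered. The figures above assume both the count and the planning rates, and the Amendment 7 rationale calls those rates too conservative.

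**I04B may be only shorthand.** The row is taken from edit-check specifications that are not in the documents, and the programmed check may be correct. This stands: the row is wrong as worded, but no actual misclassification is shown.

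**Conclusion.** Wrong as written, and minor. SAP Table 3-1 narrows the FAS below the definition in protocol 9.1, so the primary and key secondary tests would not run on the protocol's population if any dosed patient has E01 or I03. No bias is claimed.

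Under the assumption of 1 to 4 removals from 190 and the planning rates, the cost is at most about one percentage point of power. The 16.36 threshold in SAP 9.1 governs only an early stop of the Core Phase. Otherwise, according to the Amendment 7 summary of changes to section 9.6, the study runs until all patients complete two years. On the early-stop route, information of about 16.36/(1 − 0.0265) = 16.81 at stopping would absorb even the worst case tabulated.

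I04B is a secondary wording error confined to supportive PPS analyses. A reader might infer that most patients would leave the PPS; six of seven logical combinations is not a proportion of patients, and the documents do not support that.

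**What to change.** Before unblinding:

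1. In SAP Table 3-1, delete the FAS mark for E01 and I03 and keep the PPS mark, so that the FAS matches protocol 9.1. If wanted, add a sensitivity analysis of the primary endpoint without these patients.
2. If the sponsor prefers to keep the exclusion, state it in the FAS definition of both documents, limit it to blinded, pre-randomisation information, and also run the primary model on all randomised, dosed patients.
3. State the I01 no-consent exception in the FAS definition.
4. Reword I04B so that it flags only a patient who fails all three routes: fewer than one relapse in the previous year *and* fewer than two in the previous two years *and* no Gd-enhancing lesion within six months before randomisation. Count relapses back from screening, as the criterion does, and confirm that the edit-check code agrees.

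The first option costs two table cells; items 3 and 4 cost one sentence, one line of deviation wording and a code check. The second option needs matching text in both documents and one more model run. Neither needs new data.

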4.1 Inclusion criteria

Core Phase:

Patients eligible for inclusion in this study have to fulfill all of the following criteria:

1. Written informed consent must be obtained before any assessment is performed.

2. Male and female patients aged 10-17 years old*, inclusive (i.e., have not yet had their 18th birthday) at randomization.
3. A diagnosis of MS as defined by the revised consensus definition for pediatric MS, ([Krupp et al 2013](#), [Polman et al 2011](#)).
4. Central review of the diagnosis of pediatric MS will be required for all patients prior to randomization.
5. At least one MS relapse/attack during the previous year or two MS relapses in the previous two years prior to screening or evidence of one or more Gd enhancing lesions on MRI within 6 months prior to randomization (including screening MRI).
6. Expanded Disability Status Scale (EDSS) score of 0 to 5.5, inclusive.

*Exception: If, in a specific country, use of interferon- β -1a IM in children below a certain age is included in the Contraindications section of Avonex (interferon- β -1a IM) local product information, inclusion of such patients is not permitted in that country. E.g. the Russian Avonex product information lists use in children below the age of 12 years as a contraindication.

Fingolimod Extension Phase:

Criterion applies to all patients entering the Extension Phase.

1. Patients that originally met Core Phase Inclusion criteria and completed the Core phase on or off of study drug.

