A neuroradiologist will be responsible for:

- Previewing each MRI scan performed for the study patients
- Contacting the Primary Treating Physician in case of unexpected findings detected on the MRI scan

Ophthalmologist

- The Ophthalmologist will perform the ophthalmic examinations as per protocol

Pulmonary Function Test Laboratory Technician

- Pulmonary function test (PFT) technician will perform PFTs per local standard practice for pediatric patients

6 Visit schedule and assessments

The Core Phase will consist of two periods: a pre-randomization period consisting of screening and baseline visits, and a double-blind treatment period. The Extension Phase consists of a fingolimod treatment period.

The day of randomization in the Core Phase is defined as Day 1 of the study (Visit 3), which is the first day of study drug administration. Entry in the Extension Phase occurs at Visit 15 immediately following the completion of the Core Phase.

[Table 6-1](#), [Table 6-2](#) and [Table 6-3](#) lists all assessments and indicates with an “X” the visits when they are performed.

Patients should follow the visit schedule with an allowed visit window as follows:

- ± 2 days for Visit 4 and Visit 16
- ± 5 days for Visit 5 and all monthly visits
- ± 10 days for all quarterly and biannual visits
- + 14 days for Visit 15 (should be completed within 14 days of completion of Visit 14 / EOS-CP). Date of completion of Core Phase should be entered in the Study phase completion eCRF (date entered should be 1 day before Visit 15; first Extension Phase visit). Study drug should not be interrupted between the end of the Core Phase and the start of the Extension Phase.

Visit windows can be extended on a case-by-case basis to accommodate scheduling (please consult Sponsor for approval). The pre-randomization period may be extended with approval from the sponsor on a case by case basis to accommodate additional time needed to complete the screening assessments (e.g., additional lab tests, time to be (re)vaccinated, time to allow lab parameters to come within protocol requirements, etc.).

In addition to the scheduled visits, patients may have unscheduled visits following an onset of an MS relapse or for safety follow-up.

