9.4.2 Statistical model, hypothesis, and method of analysis

The null hypothesis for the primary analysis states that: there is no reduction in the annualized relapse rate (ARR) in the patients treated with fingolimod compared to the ARR in patients treated with IFN β -1a, while the alternative hypothesis states there is a reduction in the ARR in fingolimod treated patients.

The test of the hypotheses will be based on a negative binomial regression model with log link, using treatment, number of relapses in the previous two years prior to screening, pubertal status, and region as covariates. Study centers are consolidated by country. In order to minimize the impact of low-enrolling countries on the analysis (such as non-convergence of the analysis model), countries will be pooled into regions based on geographical proximity. Details will be provided in the statistical analysis plan prior to database lock.

The response variable for this analysis is the number of confirmed relapses for each patient, and the quadratic variance estimate will be used. The natural log of (time in study for each patient) will be used as the offset to account for the varying lengths of patients' time in the study. The null hypothesis will be rejected if the observed p-value is less than the significance level of 0.05.

Model-based estimates of the ARR (aggregated over each treatment group) and its 95% confidence intervals, ARR ratio and its 95% confidence intervals and p-value comparing fingolimod vs. IFN β -1a will be provided.

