4.2.1 Primary analysis

The null hypothesis for the primary analysis states that: there is no reduction in the annualized relapse rate (ARR) in the subjects treated with fingolimod compared to the ARR in subjects treated with IFN β -1a, while the alternative hypothesis states there is a reduction in the ARR in fingolimod treated subjects.

The test of the null hypothesis will be based on a negative binomial regression model with log link, using treatment, pubertal status (the stratification factor in IVRS), and region as factors and number of relapses within the previous two year before randomization as covariate. The primary analysis will be conducted on the FAS.

The response variable for this analysis is the number of confirmed relapses for each subject, and the quadratic variance estimate will be used. The natural log of (time in study in years for each subject) will be used as the offset to account for the varying lengths of subjects' time in the study. The null hypothesis will be rejected if the observed p-value is less than the significance level of 0.05.

Model-based estimates of the ARR (Least-squares mean, LSMean) and its 95% confidence intervals, ARR ratio and its 95% confidence intervals and p-value comparing fingolimod vs. IFN β -1a will be provided. The LSmean will be estimated with the OBSMARGINS option (abbreviated OM). The OM option allows the LSMEANS estimation to use the observed marginal distribution of the categorical covariates (region, pubertal status) rather than assuming equal weighting among the levels for each categorical covariate. Specification of the OM option will not affect the between-group comparison, i.e., p-value.

To control for the overall type-I error rate, a multiplicity adjustment as specified in [Section 4.2.2.1](#) will be applied to the primary and key secondary endpoints hypothesis testing. The 95% confidence intervals will not have any further adjustment for multiplicity.

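### SAP deviation I04B counts qualifying relapses back from randomisation, but the inclusion criterion counts them back from screening, so correctly enrolled patients can be dropped from the per-protocol set

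*SAP*

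**What the plan says.** **Eligibility.** Protocol 4.1, inclusion criterion 5 (criterion 4 in the synopsis), offers three alternative routes. The two relapse routes are "At least one MS relapse/attack during the previous year or two MS relapses in the previous two years prior to screening". The third is "evidence of one or more Gd enhancing lesions on MRI within 6 months prior to randomization (including screening MRI". One sentence thus uses two anchors: screening for relapses and randomisation for Gd lesions.

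**Deviation.** SAP Table 3-1, row I04B, reads "Number of relapses within: 1 yr prior to randomization is < 1, or 2 yrs prior to randomization is < 2", followed by "or 6 mths no Gd lesions". Both relapse windows run back from randomisation. The row excludes from the PPS only.

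**The interval.** Protocol Section 6 says "The pre-randomization period may be extended with approval from the sponsor on a case by case basis". Its examples include time for (re)vaccination and for laboratory values to come into range. Appendix 3, Section 15.6, requires one month between the last varicella vaccine dose and randomisation, and at least four weeks for measles, mumps and rubella.

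**Covariate.** Protocol 9.4.2 specifies the primary model "using treatment, number of relapses in the previous two years prior to screening, pubertal status, and region as covariates". SAP 4.2.1 has "number of relapses within the previous two year before randomization as covariate". The protocol synopsis counts to study enrolment, which the glossary ties to consent. The SAP 3.5.1 baseline summary counts back from the randomisation visit.

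**The concern.** A deviation that polices an inclusion criterion should be its negation. I04B tests a different rule from the one sites enrolled under. If relapses are counted to a later date, the oldest ones drop out of the window and any relapse between screening and randomisation comes in.

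Two things are at stake. First, the PPS carries the supportive relapse-rate analyses (confirmed relapses, and all relapses) and the supportive analysis of new or newly enlarged T2 lesions. Those wrongly removed would be patients whose qualifying relapse is oldest, so the loss is not random with respect to prior disease activity. Second, SAP 3.3 reports deviations that lead to PPS exclusion, so correctly enrolled patients would appear in the study report as entry violations.

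The covariate is a separate matter. It plays no part in classing patients as eligible. The point there is only that the documents describe one model term with different windows.

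**Working it through.** The plan gives no figure for this point, so there is nothing to reproduce. The check has two parts.

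**1. Worked cases.** Assume a 30-day gap from screening to randomisation, no Gd lesion, and windows of 365 and 730 days. Read I04B as flagging when all three routes fail.

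| Relapse timing | Protocol 4.1 | Days before randomisation | I04B |
|---|---|---|---|
| One, 350 days before screening | Eligible | 350 + 30 = 380 (over 365) | Flagged |
| Two, 400 and 715 days before screening | Eligible (two in two years) | 430 and 745; only one within 730 | Flagged |
| One, 10 days after screening | Not eligible | 30 − 10 = 20 | Not flagged |
| One, 100 days before screening | Eligible | 130 | Not flagged |

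The first three rows are errors; the fourth shows that a relapse well inside the window is unaffected.

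**2. Size.** None of these inputs is in the documents: Poisson relapse history at λ = 0.5, 1 or 2 per year; gap of 14, 30, 60 or 90 days (g = days/365); Gd-positive share 50%, independent of relapses. The assessment schedule with the nominal screening length is not in the text available to me, so the gap is a range.

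- Probability of failing both relapse routes: no relapse in the most recent year and at most one in the year before. q = e^(−2λ)(1 + λ). This gives 0.5518, 0.2707 and 0.0549 for λ = 0.5, 1 and 2.
- A patient who fails at screening still fails at randomisation only if no relapse falls in the gap, which has probability e^(−λg).
- The chance of failing is q at either anchor, so P(eligible at screening but flagged) = q − q·e^(−λg) = q·u, with u = 1 − e^(−λg).
- Wrongly flagged, among relapse-eligible patients without Gd lesions: q·u/(1 − q).
- Wrongly flagged, among all eligible patients: 0.5·q·u/(1 − 0.5·q).

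| λ | Gap (days) | u | No Gd lesion | All eligible |
|---|---|---|---|---|
| 2 | 14 | 0.0738 | 0.0549 × 0.0738 / 0.9451 = 0.4% | 0.02747 × 0.0738 / 0.9725 = 0.2% |
| 1 | 30 | 0.0789 | 0.2707 × 0.0789 / 0.7293 = 2.9% | 0.13534 × 0.0789 / 0.8647 = 1.2% |
| 0.5 | 90 | 0.1160 | 0.5518 × 0.1160 / 0.4482 = 14% | 0.2759 × 0.1160 / 0.7241 = 4.4% |

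The first and last rows are the extremes of the grid. Applied to 190 patients, 0.2% to 4.4% is 0.4 to 8.4, so roughly 0 to 8.

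In the other direction, a patient who fails both relapse routes and has no Gd lesion escapes the flag with probability u, which runs from 1.9% (λ = 0.5, 14 days) to 39% (λ = 2, 90 days). This matters only for a patient randomised in error.

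If the relapse windows are anchored at screening, the Gd window at randomisation, and the flag set only when all three fail, I04B is the logical negation of the criterion. Misclassification is then zero in both directions.

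**The case against.** Several stronger readings are tempting, and the documents do not support them.

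- **Ineligible patients pass.** A reader might infer this without qualification. As printed, I04B joins its conditions with *or*. On that literal reading a patient passes only with a Gd lesion, and a Gd lesion alone confers eligibility (taking I04B's six months as before randomisation). No ineligible patient then passes. The escape case needs the intended reading, and also a site that randomises someone failing a criterion although Protocol 5.3 requires all criteria to be confirmed first.
- **Many patients are lost.** If relapse dates are spread evenly over the year, the share wrongly flagged among patients who qualify by one relapse alone is the gap in months divided by 12: 1/12 = 8% at one month, 3/12 = 25% at three. That is an upper bound, because a relapse during the gap removes the flag, and it applies to a subgroup of unknown size without Gd lesions.
- **The primary result is biased.** I04B does not touch the FAS. Exclusion on pre-randomisation history does not depend on arm, and no bias in the treatment comparison has been shown.
- **The SAP covariate is wrong.** The protocol itself words the window in two ways, the SAP counts to randomisation throughout, and relapses counted to either date precede treatment. Either is a valid baseline.

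Two further objections stand. Re-anchoring alone is not enough: read literally, the *or* wording would flag 57% to 86% of eligible patients under the same assumptions, so the connectives must change too. And Table 3-1 is taken from Edit Check Specifications that are not available here; the printed row may abbreviate what is programmed.

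**Conclusion.** The mismatch is real and the concern holds in limited form. I04B, followed as written, can drop correctly enrolled patients from the PPS and report them as entry violations. This is confined to patients without a qualifying Gd lesion whose deciding relapse sits near a window edge, and it grows with the length of the pre-randomisation period. On the all-routes-failed reading, about 0.2% to 4.4% of eligible patients would be wrongly flagged. That range rests wholly on assumed relapse rates, gaps and Gd share. The supportive PPS analyses and deviation counts are affected; the FAS primary analysis loses nobody.

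The covariate discrepancy is a minor inconsistency between documents, to be settled by choosing one window. It is not an error in the model.

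**What to change.** Reword I04B in SAP Table 3-1, and the matching edit check, so that it flags a patient only if all three hold:

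1. no relapse in the year before screening; **and**
2. fewer than two relapses in the two years before screening; **and**
3. no Gd lesion in the six months before randomisation, including the screening MRI.

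Separately, state one window for the prior-relapse covariate in Protocol 9.4.2, the synopsis, every SAP section that uses it (4.2.1, Tables 4-1 and 4-2, 4.2.2.3.1, 10.1.1.1) and the SAP 3.5.1 summary. The choice should follow what the eCRF can support. SAP 3.5.1 shows relapse counts before the randomisation visit and an onset date for the most recent relapse, but does not show that every relapse date is held. If it is not, a two-year count to screening cannot be rebuilt, and amending the protocol wording is the practical course. The same check applies before the I04B flag is re-derived.

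The cost is a wording change to the SAP and deviation specification, a re-derivation of one flag where the dates allow it, and no new data. Both changes should be made before unblinding, when the SAP requires major deviations to be settled.
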